6.12.2 Treatments of Clinical (Symptomatic) Vasospasm

The treatment of clinically symptomatic cerebral vasospasm will be performed per the usual SOC at each institution.

Generally speaking, frequent neurological and clinical evaluation supplemented by transcranial Doppler (TCD) monitoring is ideal for the evaluation of cerebral vasospasm. Considering all patients enrolled in this study will be “Good-Grade Patients at High Risk of Vasospasm” (per NCS consensus recommendations) patients may also benefit from monitoring with CTA/CTP or DSA even in the absence of detectable clinical symptoms and this argument could justify performing one of these imaging modalities during the peak vasospasm window as the SOC (Recommended for this study). Any CTA / DSA / MRA imaging performed in the peak vasospasm window or performed because of a high suspicion for vasospasm should be submitted to the imaging core lab for assessment as part of this study. Consensus recommendations for monitoring with TCD threshold sensitivities are < 120 cm/s for the absence of large artery vasospasm and >200 cm/s and / or an MCA/ICA (Lindegaard) ratio >6 for the presence of large artery vasospasm.

The development of new focal neurological deficits (e.g., pronator drift), change in level of consciousness not otherwise explainable, or a significant increase in TCD velocities or Lindegaard ratio should necessitate an angiographic study to help confirm the

development of arterial vasospasm and help direct therapy or therapy should be directly administered as per the Consensus Recommendations by the Neurocritical Care Society (*Neurocrit Care* 2011). When patients develop symptoms of delayed cerebral ischemia and in whom elective angiographic imaging has already been performed, initiation of medical / endovascular therapy to reverse delayed cerebral ischemia without additional imaging is reasonable (Consensus Recommendations, NCS).

For purposes of database documentation, this study will track vasospasm “Rescue Therapies”. Triple H (Hyperdynamic) therapy protocols will be used per SOC at each clinical site. For this study, hyperdynamic therapy (i.e., Hypervolemia, Hypertension) to treat clinically symptomatic cerebral vasospasm will be considered one of three “rescue therapies”.

“Rescue therapies” include:

- Hypervolemic hyperdynamic - Fluid boluses of 500 cc or more or increases in the hourly intravenous fluid rate of more than 50% for the purpose of treating clinically symptomatic cerebral vasospasm
- Hypertensive hyperdynamic - a goal systolic blood pressure (SBP) of 160 mm Hg or more is achieved with vasopressors or inotropic medications for the purpose of treating clinically symptomatic cerebral vasospasm.
- Endovascular treatment by intracranial balloon angioplasty and / or intraarterial vasodilators (such as verapamil, nicradipine, etc.) for the purpose of treating clinically symptomatic cerebral vasospasm.

“Rescue therapies” DO NOT include:

- Allowing the SBP to naturally rise above 160 without measures such as vasopressor or inotropic medications
- Volume expansion or inotropic or vasopressor drug usage for purposes of treating decreased cardiac output or hypotension that is not associated with the treatment of symptomatic clinical vasospasm (i.e., volume or pressure support for the treatment of sepsis)

All rescue therapies initiated for the treatment of symptomatic clinical vasospasm will be documented including the symptoms associated with the clinical vasospasm, the time of onset of symptoms, duration of symptoms, resolution of symptoms, type(s) of rescue therapy utilized, other cause exclusionary testing results (i.e., CT of head showing no hydrocephalus), and TCD or angiographic data supporting the diagnosis (if available).

6.12.3 Anti-epileptic Medications

Phenytoin (Dilantin) usage is reported to be associated with decreased cognitive outcomes in aSAH patients (Naidech AM et al. *Stroke* 2005;36:583-587). Considering the primary exploratory clinical efficacy outcome of this study is a cognitive measure, the utilization of anti-seizure medications must be considered. Patients with a previous history of epilepsy should not be part of this study based on the exclusion criteria.

Per the consensus recommendations of the Neurocritical Care Society on seizure prophylaxis in aSAH patients, **routine use of anticonvulsant prophylaxis** with phenytoin (Dilantin) or fosphenytoin (Cerebyx) **is not recommended** (low quality of evidence – strong recommendation) **and is strictly prohibited by this protocol**. If indicated and anticonvulsant prophylaxis is used, a short course (3-7 days) is recommended and this will be documented on the patient eCRFs. In patients who suffer seizure after presentation, anticonvulsants should be continued for a duration defined by the local SOC but our preference is to avoid phenytoin / fosphenytoin if possible.

- All anti-epileptic medications, doses, and treatment durations should be documented in the CRFs. All seizure episodes or high suspicion seizure episodes should be documented. All EEG monitoring results should be recorded including type and time of EEG recording. For patients who have had a seizure and require anti-epileptic therapy, we prefer the usage of valproic acid or Keppra over phenytoin or fosphenytoin for the reasons mentioned above.
- Status Epilepticus (SE) is considered a neurological emergency and should be treated according to well-established protocols, guidelines, and/or the SOC at each clinical site. It is not the intention of this protocol to influence the standard emergent treatment for (SE).

6.12.4 Anti-thrombotic and Anticoagulation Medications

Anti-platelet medication therapy prior to aneurysm coiling or after aneurysm coiling is not SOC and will not be permitted. However, a single dose of aspirin (325 mg or less) at the time of the coiling procedure (if SOC for the interventionalist) will be permitted when used to prevent intraprocedural thrombotic complications.

Intravenous administration of unfractionated heparin immediately prior to or during the coiling procedure is permissible per the site's SOC, but should NOT be continued after the procedure except as determined by randomization to the LDIVH treatment arm. Following the coiling procedure, practitioners will not use anti-platelet medications in either study arm during the study drug infusion period. If the need to place patients on antiplatelet medications following the aneurysm procedure is known prior to randomization this would exclude the patient from enrollment. We prefer these medications not to be given until after the 90-day follow-up, however, if they are felt to be necessary prior to the 90-day follow-up (i.e., to prevent continued thrombotic complications), their administration will need to be documented and recorded as a study

deviation. These patients will remain in the study and their outcomes will still be recorded.

UFH (or heparin analog) infusion, injection, or other route of administration will not be permissible during this study [except as allowed by this protocol] unless it is required to treat an identified DVT or PE or other potentially serious medical condition that requires anticoagulation per usual SOC. If intravenous anticoagulation is required in the LDIVH treatment group during the infusion period, then the LDIVH infusion will be stopped and replaced with anticoagulation therapy per SOC.

6.12.5 Deep Venous Thrombosis (DVT) Prophylaxis

To reduce the chance of bleeding complications, subcutaneous chemical DVT prophylaxis will not be allowed for the LDIVH treatment arm during the duration of the LDIVH infusion. All study patients will receive mechanical DVT prophylaxis using sequential compression devices (SCDs) and preferably with TED stockings during the entire study drug infusion period.

Chemical DVT prophylaxis will be resumed as needed following the completion of the LDIVH infusion.

Chemical DVT prophylaxis of 5000 units of unfractionated heparin administered subcutaneously twice per day which will correspond to a SOC treatment will be provided to all patients randomized to the control arm of this study (The dose of UFH may be higher in patients with elevated BMI, according to each site's SOC).

Lower extremity venous duplex DVT surveillance is recommended on all study patients prior to or soon after enrollment and at least weekly during study drug infusion time period (LDIVH and Controls) for a total of at least two LE venous duplex testing results (initial and at least 1 more 7 days later). This recommended (but not required) surveillance will be considered part of the SOC for each clinical site and will not be funded by the study.

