1. STUDY SYNOPSIS AND OBJECTIVES

1.1 STUDY SYNOPSIS

STUDY TITLE	Aneurysmal Subarachnoid hemorrhage Trial RandOmizing Heparin (ASTROH)
PRIMARY OBJECTIVES	The primary objective of this study is to investigate the safety and clinical effect of a continuous low-dose intravenous unfractionated heparin (LDIVH) infusion for the prevention of aneurysmal subarachnoid hemorrhage (aSAH) induced neurocognitive dysfunction. The rate of “Major Bleeding” or “Clinically Relevant Non-Major Bleeding” as defined by the International Society of Thrombosis and Haemostasis (ISTH) between the LDIVH and the control group will be compared. The mean Montreal Cognitive Assessment (MoCA) scores obtained at a 90-day follow-up visit will be compared between LDIVH treated patients and controls. We expect the results of this study to inform on whether a properly powered Phase III study evaluating a LDIVH infusion for aSAH is warranted.
SECONDARY OBJECTIVES	Increased blood and CSF levels of certain inflammatory biomarkers have been correlated to aSAH patients with poor clinical outcomes. Unfractionated heparin (UFH) has known anti-inflammatory actions. As a result, a secondary objective of this study will be to evaluate whether LDIVH can reduce blood and CSF inflammatory biomarker levels compared to controls and whether there is any association between inflammatory biomarker levels and cognitive outcomes in aSAH.
STUDY DESIGN	Investigator initiated and sponsored, multicenter, prospective, 1:1 randomized, open-label, blinded adjudication phase II study. Study patients randomized to the LDIVH arm will receive normal standard of care (SOC) plus a continuous low-dose intravenous infusion of UFH for up to 14 days. During the 14-day infusion, the LDIVH arm study subjects will not receive any chemical deep venous thrombosis

	
(DVT) prophylaxis but may resume chemical DVT prophylaxis after the 14-day infusion is complete. Study patients randomized to the control arm will receive the normal standard of care (SOC), which will be UFH 5,000 units, twice daily.

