1.2.2 Secondary Objectives

1. Measure the correlation between blood / CSF levels of inflammatory biomarkers (e.g. hsCRP, IL-6) and cognitive function (MoCA).
2. Demonstrate a reduction in blood / CSF levels of inflammatory biomarkers (e.g. hsCRP, IL-6) in the LDIVH treated subjects compared to controls.
3. Demonstrate a reduction in cerebral vasospasm in the LDIVH treated subjects compared to controls by measuring the proportion of patients in each group who:
 - i. Demonstrate moderately severe or severe angiographic vasospasm by CTA or DSA obtained within the prime vasospasm window
 - ii. Demonstrate moderately severe or severe vasospasm on transcranial Dopplers (TCDs)
 - iii. Demonstrate vasospasm related CT infarctions
4. Demonstrate a reduction in “Delayed Cerebral Ischemia” as defined by the Neurocritical Care Society:
 - i. Symptoms of neurological deterioration (e.g., hemiparesis, aphasia, altered consciousness) presumed to be related to ischemia
 - ii. Symptoms persist for more than one hour
 - iii. Symptoms cannot be explained by other physiological abnormalities
5. Demonstrate a reduction in the need for “rescue therapy” for delayed cerebral ischemia and / or symptomatic cerebral vasospasm
6. Demonstrate a difference between the LDIVH treated subjects and controls in the proportion of patients in each group who:
 - i. Have any fever (Temperature $\geq 38.3^{\circ}\text{C}$ / 101.0°F)
 - ii. Have multiple fevers (≥ 3 fever episodes)
7. Demonstrate a significant difference in “fever burden” between LDIVH treated subjects and control subjects
8. Demonstrate a difference between LDIVH treated subjects and controls in mean Daily Fever Burden during the LDIVH infusion.

9. Demonstrate better clinical outcomes in the LDIVH treated subjects compared to controls with one of the following measures:
 - i. mRS at 90 days and 1-year (Ordinal Regression Analysis)
 - ii. Barthel Index at 90 days
 - iii. Center for Epidemiologic Studies Depression Scale (CES-D) at 90 days and 1-year
 - iv. QOLIBRI-OS at 90 days and 1-year
 - v. Lawton IADLs at 90 days
 - vi. Trail Making Test Parts A&B at 90 days
 - vii. Return to Work Status at 90 days and 1-year
 - viii. MoCA at 1-year
10. Perform Pre-specified Subgroup Analysis of Outcome measures for LDVIH and Control groups using the following subgroup designations:
 - i. Sex (Male versus Female)
 - ii. Admission CT Hijdra Sum Score (<23 versus ≥ 23)

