 - iii. Aneurysm location (ACoA Aneurysm location vs. all others; any location; anterior circulation versus posterior circulation)
 - iv. Infection requiring Antibiotic Treatment versus no infection
 - v. Elevated hsCRP at enrollment vs. normal levels at enrollment
 - vi. WFNS 1 vs. 2
 - vii. Modified Fisher grade 3 and 4 while excluding accidental enrollments with Modified Fisher not equal to 3 or 4
 - viii. Chemical DVT prophylaxis: UFH 5000 units twice daily, or increased dose in obese patients according to SOC
 - ix. LDVIH arm: LDIVH infusion >10 days vs. ≤ 10 days
 - x. LDIVH arm: Initiation of LDIVH within 48 hours of hemorrhage ictus vs. > 48 hours
 - xi. LDIVH arm: Anti-Xa (Infusion Day 6) value < 0.20 IU/mL vs. ≥ 0.20 IU/mL
 - xii. Vasospasm related CT infarction vs. No vasospasm related CT infarction
 - xiii. Tobacco smoking versus no tobacco smoking

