All subjects will receive mechanical DVT prophylaxis with sequential compression devices and / or TED Stockings per the usual SOC at each site. Compliance with this prophylaxis will be documented. Control subjects should additionally receive chemical DVT prophylaxis (5000 units of heparin subcutaneously twice daily) which will be considered within the range of SOC for each clinical site. LDIVH subjects will not receive chemical DVT prophylaxis while actively receiving the study drug. All LDIVH subjects will receive chemical DVT prophylaxis following cessation of the study drug infusion until discharge or ambulatory per the usual SOC at each clinical site. Subjects will undergo DVT / PE screening / assessment per the usual SOC at their facility, although we recommend screening by weekly lower extremity venous duplex as aSAH patients have been reported to have deep venous thrombosis in up to 20% and this may serve as justification for modifying the local SOC. Other heparin drug(s) and heparin coated catheters and devices will not be utilized in this study except for treatment of an urgent or emergent medical condition requiring heparin (eg. DVT, PE, dissection) or as mentioned above, for chemical DVT prophylaxis.

All patients should be monitored for the development of heparin induced thrombocytopenia with daily CBCs (platelet counts) and per the guidelines of the American Society of Hematology:

https://www.google.com/url?sa=t&rct=j&q=&esrc=s&source=web&cd=4&ved=0CD0QFjADahUKEwjuqvWcil3HhAhWEJR4KHWNbCp4&url=http%3A%2F%2Fwww.hematology.org%2FClinicians%2FGuidelines-Quality%2FQuick-Ref%2F529.aspx&ei=rXK_Va6qNITLeOO2qfAJ&usq=AFQjCNF64VDAzo5VXjZEKiWau t2Xmep7iA&bvm=bv.99261572,d.dmo

Daily CBCs will be considered SOC for this study. Potential HIT cases will be evaluated per recommended protocols and SOC at each site based on the guidelines above. Any case (or suspected case) of type II heparin induced thrombocytopenia (Heparin Induced Thrombocytopenia and Thrombosis - HIT) will be treated by stopping the study drug infusion in LDIVH subjects and otherwise treated per the usual SOC at each clinical site. These events will be documented in the adverse event reporting system.

Routine clinical blood work will be drawn per each site's SOC.

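### The control heparin dose is stated both with and without a BMI exception, and the subgroup built on it (item viii) can neither give a randomised treatment effect nor separate dose from body weight.

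*Protocol*

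**What the plan says.** Four places in the protocol describe the control arm's chemical DVT prophylaxis.

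- Section 1.1 (synopsis, study design) describes the control standard of care as that "which will be UFH 5,000 units, twice daily". No exception is attached.
- Section 3 gives controls "5000 units of heparin subcutaneously twice daily", again with no exception, though it is phrased as something controls should receive and as falling within each site's range of standard care.
- Section 6.12.5 gives the same dose and adds in brackets: "The dose of UFH may be higher in patients with elevated BMI", as local standard care dictates.
- Section 1.2.2, item 10 viii, lists as a subgroup "Chemical DVT prophylaxis: UFH 5000 units twice daily, or increased dose in obese patients according to SOC".

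Item 10 is introduced with the words "Perform Pre-specified Subgroup Analysis of Outcome measures for LDVIH and Control groups". Items ix, x and xi each begin with a label restricting them to the LDIVH arm. Item viii has no such label.

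For the test arm, Section 3 states: "LDIVH subjects will not receive chemical DVT prophylaxis while actively receiving the study drug". The synopsis and Section 6.12.5 agree on that. After the infusion, Section 3 gives prophylaxis to all LDIVH patients, Section 6.12.5 makes it depend on need, and the synopsis only permits it.

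**The concern.** There are two linked problems.

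First, the comparator is itself heparin, and its dose is described in two ways. Neither Section 6.12.5 nor item viii gives a BMI cut-off or an upper dose. Section 6.12.4 bars heparin by any route except as the protocol allows. A site that raises the dose in a heavy control is therefore inside Section 6.12.5 but outside the dose in the synopsis and Section 3, and how to classify that patient is left unclear.

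Second, a subgroup analysis of a randomised trial is informative when each level contains patients from both arms and the level was fixed before treatment. Item viii meets neither condition during the infusion. At stake is the meaning of one prespecified subgroup. If it were reported as listed, a reader could take a difference between its levels for a heparin dose effect or for treatment-effect modification, and it would support neither.

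**Working it through.** The point rests on setting the passages side by side. The protocol gives no figure for this subgroup, so there is none to reproduce.

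**Step 1: is the dose stated consistently?** Two places carry no exception (Sections 1.1 and 3), and two carry one (Section 6.12.5 and item viii). The trigger also differs slightly: elevated BMI in one, obesity in the other. The mismatch is a general statement against an exception stated twice.

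**Step 2: who has a value of the subgroup variable, and when?**

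| Period | Control | LDIVH |
|---|---|---|
| During infusion (up to 14 days) | Standard or raised prophylaxis dose | No chemical prophylaxis |
| After infusion | Not separately described | Prophylaxis: all patients (Section 3), as needed (6.12.5), or permitted (1.1) |

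During the infusion no LDIVH patient belongs to either level, so no LDIVH-versus-control comparison exists within a level.

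**Step 3: does the post-infusion dose rescue it?** No. It is given only after the study treatment has been delivered, and only until discharge or walking. Whether a patient receives any can therefore depend on the course under treatment. For biomarkers it also comes too late: sampling is at enrollment and days 2, 4, 6 and 10 (Section 6.11), so in a patient completing 14 days every sample precedes it.

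**Step 4: does a control-only reading rescue it?** It removes the two-arm problem but leaves confounding. A raised dose is given because of body size and according to site habit. Controls on the raised dose are by construction heavier and may cluster in certain sites. A difference between levels could reflect dose, weight or site.

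**Step 5: how precise would a control-only contrast be?** This is an illustration only.

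Inputs from Section 10.1 are 40 evaluable controls, control SD 7.0, LDIVH SD 2.5, one-sided 5%, 80% power and a 3-point MoCA difference. As a check on those inputs, n = (1.645 + 0.842)² × (7.0² + 2.5²) / 3² = 37.95, or 38 per arm. Unequal-variance t-test power at 40 per arm is 80.8%. Both agree adequately with the stated 40 per arm and 80%.

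The share of controls on a raised dose is not in the protocol. I assume 10% to 50%. The detectable difference is (1.645 + 0.842) × 7.0 × √(1/a + 1/b):

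- 10% (4 v 36): 2.487 × 7.0 × 0.527 = about 9.2 points; power for 3 points about 20%.
- 50% (20 v 20): 2.487 × 7.0 × 0.316 = about 5.5 points; power for 3 points about 38%.

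So even as a within-control comparison it would be imprecise as well as confounded.

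**The case against.** The strongest reply is that this is a matter of labelling. Section 6.12.5 is the operative section, the synopsis is a summary, and Section 3 is softened by its reference to the site's range of standard care. The exception appears twice, so it looks deliberate. The heading of item 10 also covers items ix to xi, which are plainly one-arm, so it does not oblige item viii to be a two-arm contrast. The protocol nowhere says that item viii is meant to show a treatment effect. Adding a control-arm label would end the ambiguity, and the detail of a subgroup contrast can be left to an SAP.

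Much of this stands. The dose mismatch is minor, and the purpose of item viii is undefined rather than declared wrong. What does not stand is that a label is enough: a control-only split would still confound dose with weight and site practice.

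Three stronger readings may tempt a reader, and the documents do not support them.

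- That a prophylaxis dose exists in the control arm only. Section 3 gives chemical prophylaxis to all LDIVH patients after the infusion; the gap is confined to the infusion period.
- That the spread of control doses goes undocumented. No text says the dose is unrecorded, and a subgroup on it presupposes a record. Anti-Xa is also measured in both arms at enrollment and day 6, with aPTT in controls on day 6 (Section 6.9).
- That raised control doses blur the heparin contrast between arms by some known amount. The protocol gives neither the raised dose nor the share of controls affected, and total units of intermittent subcutaneous heparin set against an aPTT-titrated infusion do not measure that contrast.

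**Conclusion.** The point holds in a limited form. The control dose is described inconsistently across Sections 1.1, 3, 6.12.5 and 1.2.2, and these must be reconciled. Item viii, as listed, cannot yield a randomised treatment effect within its levels, because during the infusion one arm has no value and the other arm's value follows randomisation. Nor can it separate dose from weight, even when read as control-only.

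This conclusion rests on the text and needs no assumption about how many controls receive a raised dose; only the precision illustration does. The effect on the trial is small. Item viii is one of 13 subgroup designations under the secondary objectives, study success in Section 1.1 does not refer to it, and the primary MoCA analysis, randomisation and sample size are unaffected. I take no view on which dose wording is right.

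**What to change.** 1. Reconcile the control prophylaxis wording in Sections 1.1, 3, 6.12.5 and item viii, so that all four either carry the exception or omit it. The choice is the sponsor's. Align the three statements on LDIVH prophylaxis after the infusion at the same time.
2. Replace item viii with a baseline weight or BMI category, with its cut-off fixed in advance and defined identically in both arms. Each level then contains randomised patients from both groups.
3. Report the control prophylaxis dose actually received as a descriptive table for the control arm, without a test presented as a treatment or dose effect.

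The cost is wording in a few sections and one redefined subgroup. Weight is needed for dosing per kilogram in the LDIVH arm, but its recording in controls must be confirmed, as must height in both arms if BMI is used. The redefined subgroup asks whether the treatment effect varies with body size. That is a different question from prophylaxis dose, but one the randomised design can address, subject to the low precision of any subgroup in a trial of 88 patients.
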